- Day 24-26 (2 overnight stays in clinic): Subjects return to clinic prior to last evening dose on Day 24 for pre-dose PK blood collection. Blood collections occur post final dose on Day 24 for PK. All subjects will have breakfast 30 minutes prior to final dose on Day 25. Extensive PK blood sampling, urine collections and Holter monitoring occur pre and post final dose on Day 25, with final draw 24 hours post dose (Day 26). Final discharge from clinic on Day 26 will occur after 24 hour blood draw, vital signs, ECG, haematology and biochemistry testing, serum pregnancy test for female subjects, urine for urinalysis and cotinine test, expired CO, completion of tobacco craving questionnaire, safety assessment, risks of smoking and quit advice, review of diary requirements, and reminder of post study followup visit date.
- **Post Study:** A post study follow-up visit will be conducted 6 to 8 days after last dose of cytisine. If any adverse events are recorded at post study follow up assessment, arrangements will be made with the subject, so that they are followed-up appropriately and the final outcome determined. Smoking history will be reviewed and final review of risks of smoking and quit advice provided.

The end of study is defined as completion of safety follow-up on all subjects. The maximum duration of this study is estimated to be around 9 weeks (screening to last subject's last visit).

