## **7.2. Smoking, Diet and Fluid Restrictions**

### **7.2.1. Smoking**

There will be minimal restrictions to smoking during days of confinement, such as all smoking must occur within designated area(s) only and subjects cannot smoke during active PK sampling period (i.e. subjects must have their last cigarette a minimum of 2 hours before dosing and can only start smoking after final PK sample). Subjects will go for a cigarette as a group and will need to have their last cigarette before 23:00 while they stay in the clinic. Clinic staff will review these guidelines with subjects during confinement and will monitor compliance.

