#### On Day 25:

1. All subjects to have breakfast 30 minutes prior to final dose.
2. Attach ECG Holter monitor, checking to ensure recording has started. NOTE: Holter monitors to remain attached to subjects approximately 24 hours, discontinued on Day 26.
3. Record Vital signs (supine blood pressure, pulse rate and oral temperature).
4. Obtain pre-dose PK blood sample (Section 12.1).
5. Begin urine collection for PK as outlined in (Section 12.2).
6. Subject to take final Day 25 dose of cytisine (documenting time of dose in diary) after breakfast and begin extensive PK blood and urine sampling as outlined in (Section 12.1) throughout day and up through 24 hours post.
7. Obtain 12-lead ECG (triplicate) if clinically indicated.
8. Record any adverse events and update concomitant medications.
9. The number of cigarettes smoked will be recorded in the CRF.
10. All subjects will remain in the clinic overnight.

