#### On Day 26:

1. Complete final PK blood draw and urine collection (Section 12.1).
2. Obtain blood and urine for haematology, biochemistry, serum pregnancy test (females only) and urinalysis (Section 13.4.1).
3. Vital signs (supine blood pressure, pulse rate and oral temperature).
4. 12-lead ECGs (triplicate).
5. Obtain urine for cotinine test and expired air CO prior to discharge.

6. Subject to complete tobacco craving questionnaire (see [Appendix 3](#)).
7. Record any adverse events and update concomitant medications.
8. Subject given advice about the risks of smoking and quitting.
9. Remind subject to record number of cigarettes smoked daily in diary, discharge subject from clinic and schedule follow up visit (within 6-8 days).

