11.5 PD ANALYSES

11.5.1 Number of Cigarettes Smoked and Expired CO

The number of cigarettes smoked in the past 24 hours will be recorded at Screening and daily from Day -1 to Post-Study. Expired air carbon monoxide (CO) data will be obtained at Screening and prior to discharge on days 4, 13, 17, 21 and 26.

The number of cigarettes smoked during the past 24 hours will be taken from the values recorded in the CRF (at CPU) for Screening and Day -1 to Day 3 and from the subject diaries thereafter. In order to evaluate any reduction in smoking, the number of cigarettes smoked daily will be assessed as well as smoking cessation status at Day 26. For each individual subject a smoking cessation status of 'Ceased smoking' will be defined as not having smoked any cigarettes for the past 24 hours on Day 26 and confirmed by an expired CO level <10ppm on Day 26. If these criteria are not satisfied, a smoking cessation status of 'Continued smoking' will be assigned to a subject, including subjects who have missing data at Day 26 for either the number of cigarettes smoked or expired CO level, or both.

The number of cigarettes smoked daily and smoking cessation status will be listed. Frequencies (n, %) of smoking cessation status at Day 26 will be calculated by dose group and age group. For those subjects who had ceased smoking by Day 26, frequencies of the day of first smoking cessation (defined as smoking 0 cigarettes and where cessation is sustained without relapse) will be presented by dose group and age group. Descriptive statistics (N, n, mean, SD, minimum, median and maximum) of absolute and change from baseline (Day -1) number of cigarettes smoked will be tabulated by dose group and age group. The mean absolute values and mean change from baseline will also be presented graphically. Individual subject plots of the number of cigarettes smoked daily will also be produced.

Expired CO levels will be included in the listing that presents the smoking cessation status data. Descriptive statistics (N, n, mean, SD, minimum, median and maximum) of absolute and change from baseline (Screening) expired CO results will be tabulated by dose group and age group. The mean absolute values and mean change from baseline values will also be presented graphically. Individual subject plots of expired CO levels will also be produced.

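### The Day 26 'Ceased smoking' look-back falls inside a confinement with restricted smoking, so the status may reflect compliance with clinic rules as well as cessation

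*SAP*

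**What the plan says.** **Definition.** SAP 4.1 lists cessation at Day 26 among the primary variables, and SAP 1.2 records that the SAP added it. In SAP 11.5.1 the status 'Ceased smoking' is "defined as not having smoked any cigarettes for the past 24 hours on Day 26 and confirmed by an expired CO level <10ppm". Anyone else, including a subject with a missing Day 26 count or CO, is 'Continued smoking'.

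**Where subjects are.** Protocol 11.2.11 has them check in on the afternoon of Day 24 and stay the nights of Days 24 and 25. Protocol 5.1 discharges them on Day 26 after the 24 h draw, which is sample 95 in Protocol Table 7. The Day 26 list includes "Obtain urine for cotinine test and expired air CO prior to discharge".

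**What they may smoke.** Protocol 7.2.1 calls the in-clinic limits minimal, and then states that "subjects cannot smoke during active PK sampling period". It explains this in the same sentence: "subjects must have their last cigarette a minimum of 2 hours before dosing and can only start smoking after final PK sample". It adds that subjects "will need to have their last cigarette before 23:00 while they stay in the clinic", without a time at which smoking may restart next morning. The Day 25 list nevertheless contains the item "The number of cigarettes smoked will be recorded in the CRF".

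**What is silent.** Neither document relates the cessation definition to these limits. Protocol 13.9 gives no clock time for the diary entry.

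**The concern.** A subject who has not quit but keeps to the clinic rules can record zero cigarettes for the look-back and pass the CO criterion. That subject is then reported as 'Ceased smoking'. The effects would be:

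- The cessation frequencies in Table 14.5.1.2 could be too high in absolute terms.
- The outputs split by status (Tables 14.5.1.3 and 14.5.1.6; Figures 14.5.1.3, 14.5.1.4, 14.5.1.7 and 14.5.1.8) would mix such subjects with real quitters.
- In small groups one subject carries visible weight.

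**Working it through.** The plan gives no figure for restricted hours, so there is none to reproduce. The check is the overlap between the look-back and the restricted periods.

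**Inputs**
- Look-back: 24 h, assessed on Day 26 (SAP 11.5.1).
- Bar: starts 2 h before dosing and ends after the final PK sample; last in-clinic cigarette before 23:00 (Protocol 7.2.1).
- Draws at 12 h and 24 h after the Day 25 dose (Protocol Table 7).
- Day 25 dose given in the morning (Protocol 15.6). A clock time of about 09:00 is stated for Day 1 only (Protocol 8.8). *Assumed* for Day 25: D = 8, 9 or 10.
- *Assumed*: the look-back ends d = 0 to 4 h after the 24 h draw.

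In hours from the Day 25 dose, the look-back is [d, 24 + d].

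**Reading A: the bar runs to the 24 h draw.** The bar is [−2, 24], or 26 h. The overlap is 24 − d, whatever the dose time: 24, 23, 22, 21 and 20 h for d = 0, 1, 2, 3 and 4. A look-back ending up to 2 h before the draw also gives 24 h.

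**Reading B: the bar ends at the 12 h draw and resumes at 23:00.** The daytime part is 12 − d. The night part depends on when smoking may restart, which is not stated.

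| Assumed restart | Night part (h) | Total (h) | d = 0 | d = 4 |
|---|---|---|---|---|
| After the 24 h draw | D + 1 | 13 + D − d | 21–23 | 17–19 |
| 07:00 | 8 | 20 − d | 20 | 16 |
| 06:00 | 7 | 19 − d | 19 | 15 |

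Reading B therefore spans 15–23 h, or 62.5%–95.8% of the look-back. If the delay were 6 h, Reading A would give 18 h and Reading B 13–17 h.

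**What CO adds.** A subject who truly meets the zero-cigarette criterion has had about 24 h to clear CO. The documents give no half-life; take 2–8 h as an assumption. The fraction left is 2^(−24/h): 0.02% at h = 2 and 12.5% at h = 8. At h = 8, a start of 20 ppm reads 2.5 ppm and 40 ppm reads 5.0 ppm. A start above 10 / 0.125 = 80 ppm would be needed to stay above 10 ppm. Entry requires more than 11 ppm (Protocol 6.1.1). CO can therefore expose a false zero, but it cannot separate a compliant smoker from a quitter.

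**Weight of one subject** in the planned groups (Protocol 15.4): 100/18 = 5.6 points per arm, 100/12 = 8.3 in the non-elderly and 100/6 = 16.7 in the elderly. These are weights, not estimates of the error, and they grow if the PD Set is smaller.

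**Which diary days show the problem.** Subjects are outpatients from discharge on Day 21 until the afternoon of Day 24. A cigarette on Day 24 before check-in appears on the Day 24 or the Day 25 entry, depending on when the diary is filled in. A count limited to Days 22–23 would miss it. A count over Days 22–25 that treats missing entries as positive does not, provided the diary is truthful.

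**The case against.** **The literal reading may be too harsh.** Protocol 7.2.1 speaks of minimal restrictions and of active sampling, and has subjects go out to smoke as a group. Cigarettes are recorded on Day 25 itself. Protocol Table 7 closes the Day 25 block at 12 h and lists the 24 h draw under Day 26, although SAP 11.4.1 lists it under Day 25. This stands: a continuous 26 h ban cannot be taken as settled. Under Reading B a continuing smoker has some opportunity to smoke and, on using it, is correctly classed 'Continued smoking'. Part of the night bar also falls in hours of sleep. The overlap remains substantial on either reading.

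**The SAP already offers diagnostics.** Table 14.5.1.4 gives the first day of sustained cessation among 'Ceased' subjects. Cotinine is listed with the status, and individual plots are planned. This also stands in part, and it is why only a small addition is needed. But the headline status uses none of these, and a compliant smoker whose first zero falls on Day 25 or 26 looks there like a late quitter.

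**The impact is limited.** No hypothesis test is planned (Protocol 15.4), the SAP openly defines a 24 h status, and subjects had to want to stop smoking (Protocol 6.1.1). All of this holds and limits the importance.

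**Stronger inferences.** A reader might infer that the rule biases the comparison of doses. The documents do not support this: both randomised groups face the same rule, and no direction is shown. A reader might also infer that most 'Ceased' subjects would be continuing smokers. Nothing in the documents gives compliance or the number affected.

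**Conclusion.** The concern holds in limited form. The Day 26 status is measured over hours when the clinic restricts smoking: 20–24 of 24 h if the bar runs to the 24 h draw, and roughly 15–23 h if it ends at the 12 h draw and resumes at 23:00. Both ranges assume an assessment within 4 h of the 24 h draw; the second also assumes dosing between 08:00 and 10:00 and a morning restart between 06:00 and the 24 h draw. The status may overstate absolute cessation rates and blur the subgroups built on it. The size of that effect cannot be derived from the documents. The conclusion that CO does not identify the cause of abstinence rests on the assumed half-life of 2–8 h. Importance is minor to moderate.

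**What to change.** 1. **Label.** In SAP 4.1 and 11.5.1, keep the Day 26 CO-confirmed status but call it 24 h abstinence during confinement.
2. **Count.** Beside Table 14.5.1.2, report by dose and age group how many 'Ceased' subjects have at least one cigarette, or a missing entry, on any Day 22–25 diary entry. This bounds the number whose status rests on the confinement window. Read it with Table 14.5.1.4.
3. **Sensitivity.** Add a cessation frequency that requires the Day 26 definition and zero cigarettes on all Day 22–25 entries, with missing counted as 'Continued'. Among 'Ceased' subjects, also report the diary from Day 27 to follow-up as a durability check. Follow-up is 6–8 days after Day 25, so Day 31–33, which gives 5–7 entries. The subgroup graphs need not all be repeated.
4. **Reconcile.** Clarify how Protocol 7.2.1 applies on Days 25–26, and state in the report which reading was applied.

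**Cost.** A label, one count, one derivation and one diary summary. The data are already collected, including for the non-elderly cohort whose database is locked first (SAP 9.3).

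**Downsides.** The Day 22–25 and follow-up entries are self-reported without CO confirmation. True quitters from about Day 23 on are excluded from the sensitivity status, so its rate may be lower. A Day 22 entry made in the morning can include part of the Day 21 clinic morning.

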11.5.2 Urine Cotinine

Urine cotinine data will be obtained at Screening and prior to discharge on days 4, 13, 17, 21 and 26.

Urine cotinine levels will be included in the listing that presents the smoking cessation status data. Descriptive statistics (N, n, mean, SD, minimum, median and maximum) of absolute and change from baseline (Screening) urine cotinine levels will be tabulated by dose group and age group. The mean absolute values and mean change from baseline values will also be presented graphically. Individual subject plots of urine cotinine levels will also be produced.

11.5.3 Tobacco Craving Questionnaire

The Tobacco Craving Questionnaire – Short Form (TCQ-SF) will be completed on days -1, 4, 13, 17, 21 and 26.

The TCQ-SF is a 12-item questionnaire that assesses 4 components of tobacco craving: emotionality (3 items), expectancy (3 items), compulsivity (3 items) and purposefulness (3 items). Responses to each item are scored from 1 (strongly disagree) through 7 (strongly agree). Component scores are defined

as the sum of the scores within each component. The total score is defined as the sum of the 4 component scores. If any item responses are missing then the relevant component score(s), as well as the total score, will not be calculated.

The TCQ-SF total score and component scores for emotionality, expectancy, compulsivity and purposefulness will be listed and descriptive statistics (N, n, mean, SD, minimum, median and maximum) of absolute and change from baseline (Day -1) results will be tabulated by dose group and age group. For the total score, the mean absolute values and mean change from baseline values will also be presented graphically.

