### **11.2.2. Day -1**

All subjects will check into the research facility and upon arrival to the clinic, the following procedures will be performed:

1. Vital signs (supine blood pressure, pulse rate and oral temperature).
2. Update any medical history or concomitant medications.
3. Repeat urine testing for drugs of abuse and urine pregnancy test for female subjects.
4. Obtain 12-lead ECG (triplicate).
5. Verification of eligibility criteria.
6. Record number of cigarettes smoked in past 24 hours and instruct subject how to document cigarette smoking and dosing times in the daily smoking/medication diary (see Section 13.9).
7. Subject to complete the Fagerström nicotine dependence questionnaire (see Appendix 2).
8. Subject to complete tobacco craving questionnaire (see Appendix 3).
9. Each subject given advice about the risks of smoking and quitting. This will take the form of a brief interview following WHO evidence-based recommendations on the treatment of tobacco dependence.
10. Each subject must fast for minimum of 10 hours prior to first dose on Day 1.

### 11.2.3. Day 1 to Morning of Day 4

The results of screening for each subject must be reviewed by the Principal Investigator or designee prior to randomisation to assure eligibility criteria have been met.

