### APPENDIX 3. SHORT FORM OF THE TOBACCO CRAVING QUESTIONNAIRE

The template below has been validated as a self-report instrument to measure tobacco craving and will be administered to study subjects as outlined in this protocol. Analysis of results is outlined in the study Statistical Analysis Plan.

Question	Response						
	Strongly Disagree....Strongly Agree						
Factor 1 (emotionality)							
I would be less irritable now if I could smoke.							
If I were smoking now I could think more clearly.							
I could control things better right now if I could smoke.							
Factor 2 (expectancy)							
I would enjoy a cigarette right now.							
A cigarette would taste good right now.							
Smoking a cigarette would be pleasant.							
Factor 3 (compulsivity)							
If I smoked right now, I would not be able to stop.							
I could not stop myself from smoking if I had some cigarettes here.							
Factor 4 (purposefulness)							

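### Does the 11-item craving form in Protocol Appendix 3 undermine the 12-item TCQ-SF scoring in SAP 11.5.3?

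*SAP*

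**What the plan says.** SAP 11.5.3 states that "The TCQ-SF is a 12-item questionnaire that assesses 4 components of tobacco craving". It gives each component three items, the last two being "compulsivity (3 items) and purposefulness (3 items". Each item is scored 1 to 7, and a component score adds up the item scores belonging to that component. For the total, "The total score is defined as the sum of the 4 component scores". On incomplete forms, "If any item responses are missing then the relevant component score(s), as well as the total score, will not be calculated".

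Protocol Appendix 3 prints the form and says that it "will be administered to study subjects as outlined in this protocol". It leaves scoring elsewhere: "Analysis of results is outlined in the study Statistical Analysis Plan". The Day -1 instruction in Protocol 11.2.2 reads "Subject to complete tobacco craving questionnaire (see Appendix 3", and the instructions for Days 4, 13, 17, 21 and 26 are to the same effect. Under the compulsivity factor the appendix shows two statements, the first being "If I smoked right now, I would not be able to stop", and then moves to the purposefulness factor.

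SAP 1.2 records that TCQ-SF change from baseline was added as a pharmacodynamic endpoint. It says nothing about the number of items.

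**The concern.** The protocol presents Appendix 3 as the form to be given and hands the scoring to the SAP, so the two should agree item for item. As they read, they do not: the SAP expects a third compulsivity item that the appendix does not show. Two of the five TCQ-SF scores, compulsivity and the total, depend on that item.

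Two things would be at stake if subjects really answered 11 items. First, those two scores would sit on a shorter scale than a reader of the SAP would assume. Second, a programmer who treated the absent twelfth item as unanswered could apply the missing-item rule to every form, leaving no compulsivity or total score for anyone. The scores appear under the primary variables heading in SAP 4.1, so the mismatch deserves a look.

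**Working it through.** **Item counts.** The SAP's own figure reproduces: 4 components × 3 items = 12. Counting the rows in Appendix 3:

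| Component | SAP 11.5.3 | Appendix 3 as it reads |
|---|---|---|
| Emotionality | 3 | 3 |
| Expectancy | 3 | 3 |
| Compulsivity | 3 | 2 |
| Purposefulness | 3 | 3 |
| Total | 12 | 11 |

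The difference is one item, in compulsivity. The SAP's sum is sound, so this is a disagreement between documents and not an arithmetic error.

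**Score ranges.** With items scored 1 to 7, a score built from k items runs from k × 1 to k × 7.

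- Compulsivity: 3 items give 3–21; 2 items give 2–14.
- Total: 12 items give 12–84; 11 items give 11–77.
- Largest possible change in compulsivity: 21 − 3 = 18 against 14 − 2 = 12.
- Largest possible change in the total: 84 − 12 = 72 against 77 − 11 = 66.

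SAP 11.5.3 states none of these ranges, so none of them is wrong in the plan.

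**Extent.** The form is given on six days (-1, 4, 13, 17, 21 and 26). For 36 subjects that is 36 × 6 = 216 questionnaires, of which 36 × 5 = 180 are post-baseline. Replacement subjects would add to this. The outputs concerned are the baseline TCQ-SF total (SAP 11.2.1), Table 14.5.1.8, Figures 14.5.1.11 and 14.5.1.12, and Listing 16.2.13.4.

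**If 12 items were collected.** SAP scoring applies exactly as written and no score changes. Appendix 3 either has a third item that was lost in conversion or omits it by a slip.

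**If 11 items were collected.** The component rule adds the items that belong to compulsivity, which are then two, and the total adds the four components. Both are defined without any further instruction. Changing the stated count from 12 to 11 would leave every computed value as it was. Changes from baseline and dose-group summaries use the same form on both sides, so they stay like for like.

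**The missing-item rule.** It is triggered by missing responses. An item that was never on the form produces no response to be missing, so the natural reading scores the items that were put to subjects. The opposite reading would blank the compulsivity and total columns for every subject at every visit. That could hardly escape the data review meeting and independent programming described in SAP 9.3 and 12.

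**Which count is likelier.** SAP 1.1 says the plan was developed from protocol version 2.0 and from the annotated CRF dated 4 October 2017. Its author therefore had the data-collection pages and still wrote three items per component. The protocol states no item count and calls the appendix form a template. This leans towards 12 without proving it: the CRF is not among the documents, and the table shells are redacted.

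**The case for a change.** The strongest contrary argument is that an instrument and its scoring rule should match on paper before data are locked, and that checking two pages costs almost nothing. There are also reasons to doubt a lost row. The table carries no sign of damage at that point, and the neighbouring Fagerström form in Appendix 2 came through complete, with six questions that agree with the six scored in SAP 11.8.3. With two database locks by age cohort (SAP 9.3), a scoring question settled differently at each lock could put the cohorts on different footings.

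Part of this stands. The count differs, and looking at the original appendix page and the CRF is ordinary good housekeeping. But other tables in the same text are visibly disturbed: the SAP schedule marks urine PK collection at many visits although its own footnote limits it to Days 1 and 25. One absent row is therefore thin evidence of a planning error. The two-lock risk arises only if someone departs from the written sum rule between locks, and nothing in the SAP invites that. A wrong item count in the SAP, if it is wrong, would be a descriptive slip with no numerical consequence.

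**Conclusion.** The mismatch is real in the text as it reads, at 11 items against 12, but it does not call for a change to the plan. It is at most a clerical slip in an appendix page or in one descriptive phrase of SAP 11.5.3, and under either possibility the written rule yields the same computed scores. The most it could affect is how readers interpret the scale of two TCQ-SF scores, compulsivity (2–14 rather than 3–21) and the total (11–77 rather than 12–84).

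The TCQ-SF summaries are descriptive, the endpoint was added by the SAP and is absent from Protocol 15.8, and SAP 3.5 plans no specific hypothesis testing. No PK, safety or other pharmacodynamic result depends on it.

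This conclusion assumes that one version of the form was used at all visits and in both age cohorts, and that items never administered are not counted as missing responses. The documents cannot show which count is right, and the conclusion does not depend on knowing.
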